10.1 General Conventions

According to the Close Out plan, only descriptive statistics and listings will be presented, no inferential statistics will be performed for the primary and secondary endpoint. Descriptive statistics for continuous variables will include the number of subjects, mean, standard deviation, median, minimum and maximum. Descriptive statistics for dichotomous/categorical variables will include the number and percentage of subjects. All summary tables will be presented overall. Unless specified otherwise, percentages are based on non-missing values, excluding missing data and subjects who early discontinued.

- Baseline

Baseline is defined as the last non-missing measurement prior to the index procedure.

- Study Day

Unless specified otherwise, Study Day will be calculated as the difference between the event date and the date of index procedure, i.e., event date - date of index procedure. The day of index procedure is considered as Day 0.

- Date conversion

For the purposes of statistical analyses, a month is considered equivalent to 30 days and a year is considered equivalent to 360 days.

- SAS version

All statistical analyses will be performed using SAS®, Version 9.2 or later, unless otherwise noted.

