10.4 Primary and Secondary Endpoint Analyses

Protocol specified tests of hypotheses of the primary endpoints will not be performed due to the study terminating early for low enrollment. Descriptive analyses of the primary effectiveness and primary safety endpoint will be conducted in the mITT Analysis Set. Categorical data will be summarized with exact binomial confidence intervals for primary effectiveness and safety endpoints. Continuous data will be summarized with averages by visit and as average change from baseline at each visit.

Unless specified otherwise, the classification of adverse events will be based on the data from study case reported forms (CRFs). In the event the data are not captured or are missing, the DSMB and/or CEC adjudication data will be reported.

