10.4.1.2 Primary Safety Endpoints

- Incidence of major ipsilateral stroke and/or death

The incidence of major ipsilateral stroke and/or death will be evaluated from the start of the index procedure until the completion of the 12-Month Follow-up based on the assessment from DSMB adjudicated data.

The number and percentage of subjects with major ipsilateral stroke and/or death up to and including 12-Month Follow-up will be summarized.

- Incidence of In-sent stenosis

The number and percentage of subjects with in-stent stenosis up to and including 12 months post-procedure will be summarized based on the assessment from the Independent Core Laboratory. Subjects with missing data will be excluded from analysis.

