10.4.2.2 Secondary Safety Endpoints

- Rate of new neurological deficits as per mRS

The number and percentage of subjects with new neurological deficits, not related to stroke or death, will be summarized at baseline (pre-procedure) and follow-up visits, e.g., 30 days, 6 and 12 months post-procedure. Subjects who died prior to an evaluation will have an mRS score of 6 imputed at that timepoint for analysis purpose.

- NIHSS total score

The NIHSS total score and its change from baseline will be summarized at baseline (pre-procedure) and follow-up visits (6 months and 12 months post-procedure). In addition, the number and percentage of subjects who show a worsening from baseline (an increase of 4 points or more) will also be presented. Only the observed scores will be included in summaries.

- Adverse Events and Clinical Complications

AEs from the start of the index procedure until completion of the 12-Month Follow-up will be coded using the latest version of Medical Dictionary for Regulatory Activities (MedDRA) into system organ class (SOC) and preferred terms (PTs). The number of events, the number and percentage of subjects with events and event rates by SOC and PT will be summarized for the following:

- Any AEs
- Study device or procedure related AEs
- Any serious AEs (SAEs)
- Unanticipated AEs
- AEs leading to death

AEs related to device/procedure are defined as those with the relationship of definitely, probably or possibility related. AEs with miss relationship will not be imputed. Subjects with multiple relationships on the same AE will be reported by the events of the highest relationship. Only the relationship as determined by CEC will be used in the safety analysis.

In addition, device or procedure related AEs will be presented overall and by study period as follows:

Table 2: AEs by Study Period

Study Period	Lower Bound of AE Start Date	Upper bound of AE Start Date
Peri-procedure	from the beginning of the procedure	Until 24 hours post-procedure (Day 0)
12-Month Follow-up	After 24 hours post-procedure (i.e., from Day 1)	Until the date of: 
○ early discontinuation in the study; or

Study Period	Lower Bound of AE Start Date	Upper bound of AE Start Date
		
 ○ the upper bound of the 12-Month analysis window (i.e., Day 450)

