If the AE onset day is missing but the month and year is available, then the missing day will be imputed to be Day 1 of that month as a conservative approach. As an example, if the AE has an onset date of July of 2016, with an unknown day, the imputed onset day would be 01JUL2016. If the month and/or year is unknown, then, the AE will be categorized as unknown.

- Reduced TICI Flow

The number and percentage of subjects with a reduced TICI flow (TICI score of 0 or 1) at the target vessel during the index procedure will be summarized. Subjects with missing data on this endpoint will be excluded from analysis.

- Bleeding complications

The number and percentage of subjects who experience a procedure-related hemorrhagic event which requires any of the following will be summarized:

- Blood transfusion
- Surgical intervention
- New hospitalizations
- Lengthening of hospital stay for the index procedure
- In-stent stenosis

The number and percentage of in-stent stenosis at immediately post-procedure (acute), and up to and including 6-Month Follow-up (excluding acute events) will be summarized in the same way the primary safety endpoint (in-stent stenosis) at 12-Month Follow-up.

For subjects with acute in-stent stenosis, the number and percentage of subjects who have parent vessel stenosis caused by vasospasm, and whether vasospasm was responsive to medication will be summarized based on the assessment from the Independent Core Laboratory.

- Thrombosis

The number and percentage of subjects with thrombosis up to and including 6 months and 12 months post-procedure will be summarized based on the assessment from the Independent Core Laboratory. Subjects with missing data on thrombosis will be excluded from analysis.

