10.6 Handling of Missing Data

Unless stated otherwise, missing data will not be imputed, percentages will be based on non-missing data.

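### Read literally, the SAP's default for percentages removes early discontinuers and stroke/death has no stated exception, so a non-fatal major stroke observed before withdrawal can drop out of the primary safety rate

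*SAP*

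**What the plan says.** SAP 10.1 (General Conventions) gives the default for percentages, which holds wherever nothing else is specified: "percentages are based on non-missing values, excluding missing data and subjects who early discontinued".

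SAP 10.4 names the analysis set: "Descriptive analyses of the primary effectiveness and primary safety endpoint will be conducted in the mITT Analysis Set". SAP 7 defines that set by attempted treatment, not by completion of follow-up.

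For major ipsilateral stroke and/or death, SAP 10.4.1.2 says that the incidence "will be evaluated from the start of the index procedure until the completion of the 12-Month Follow-up based on the assessment from DSMB adjudicated data", and then: "The number and percentage of subjects with major ipsilateral stroke and/or death up to and including 12-Month Follow-up will be summarized". It states no denominator and no rule for a subject who has an event and later discontinues. In the same section the other primary safety endpoint, in-stent stenosis, does have a rule: "Subjects with missing data will be excluded from analysis".

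SAP 10.6 (Handling of Missing Data) repeats the convention without naming discontinuers: "missing data will not be imputed, percentages will be based on non-missing data".

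Protocol 3.2.2.1 gives the endpoint the same cumulative window, from the start of the index procedure to completion of 12-month follow-up. Protocol 4.2.1 keeps a withdrawn subject's data for the final analysis unless the subject asks that they not be used.

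**The concern.** An adjudicated stroke before withdrawal is an observed outcome of a cumulative endpoint. Later loss of contact cannot make it missing. The default in SAP 10.1 nevertheless names two groups to leave out, missing data and early discontinuers, and the second group adds nothing to the sentence if it means only people who lack a value. Applied as written, the rule takes such a subject out of both the numerator and the denominator.

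At stake is the reported primary safety percentage and its exact interval. From the same data, one programmer could follow 10.1 to the letter and another could follow 10.6 and the cumulative wording, and they could report different rates. One of those rates would omit an observed major stroke.

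The same default reaches other cumulative event percentages that have no rule of their own: adverse events ("the number and percentage of subjects with events and event rates by SOC and PT will be summarized for the following") and bleeding complications in SAP 10.4.2.2, and recanalization and retreatment in SAP 10.4.2.1.

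**Working it through.** **Passages side by side**

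| Item | Own rule on who is excluded | Discontinuers named? |
|---|---|---|
| Default for percentages (SAP 10.1) | Missing data and early discontinuers | Yes |
| Missing data (SAP 10.6) | Missing data | No |
| Complete occlusion at 12 months (10.4.1.1) | Missing Raymond score | No |
| In-stent stenosis (10.4.1.2) | Missing data | No |
| Reduced TICI flow and thrombosis (10.4.2.2) | Missing data; for thrombosis, "Subjects with missing data on thrombosis will be excluded from analysis" | No |
| Stent movement/migration (10.4.3) | Missing data | No |
| Stroke/death (10.4.1.2) | None | Default applies |
| AEs and bleeding (10.4.2.2) | None | Default applies |
| Recanalization and retreatment (10.4.2.1) | None | Default applies |

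SAP 10.2 lists subjects who died separately from those who discontinued. A death is therefore probably not an early discontinuation, and the exposure is to non-fatal strokes.

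**Effect on the rate**

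No stated figure is in dispute. The protocol's power for this endpoint (92.5% with 150 subjects, 14% against a goal of 25%, two-sided 0.05) reproduces as 92.46% with the null-variance z formula.

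The documents give no enrolment, event or discontinuation counts, so every count below is assumed. Let N be the mITT subjects, E the subjects with an event, D the early discontinuers, and k the discontinuers with an earlier non-fatal major stroke.

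- All mITT: E/N
- Literal 10.1: (E − k)/(N − D)
- Observed events kept, event-free discontinuers left out: E/(N − D + k)

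Intervals are exact (Clopper-Pearson) 95%, the type named in SAP 10.4.

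| N, E, D | All mITT | Literal, k=0 | Literal, k=1 | Literal, k=2 |
|---|---|---|---|---|
| 30, 4, 4 | 4/30 = 13.3% (3.8–30.7) | 4/26 = 15.4% (4.4–34.9) | 3/26 = 11.5% (2.4–30.2) | 2/26 = 7.7% (0.9–25.1) |
| 60, 4, 4 | 4/60 = 6.7% (1.8–16.2) | 4/56 = 7.1% (2.0–17.3) | 3/56 = 5.4% (1.1–14.9) | 2/56 = 3.6% (0.4–12.3) |
| 50, 7, 8 | 7/50 = 14.0% (5.8–26.7) | 7/42 = 16.7% (7.0–31.4) | 6/42 = 14.3% (5.4–28.5) | 5/42 = 11.9% (4.0–25.6) |
| 160, 22, 16 | 22/160 = 13.8% (8.8–20.1) | 22/144 = 15.3% (9.8–22.2) | 21/144 = 14.6% (9.3–21.4) | 20/144 = 13.9% (8.7–20.6) |

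**Direction against the all-mITT rate.** (E − k)/(N − D) is below E/N when N(E − k) < E(N − D), that is, when k > D × E/N. The break-even values are:

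- 4 × 4/30 = 0.53
- 4 × 4/60 = 0.27
- 8 × 7/50 = 1.12
- 16 × 22/160 = 2.2

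In the first two rows a single such stroke makes the literal rate too low. In the last two it does not.

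**Direction against the events-kept rate.** Going from (E − k)/(N − D) to E/(N − D + k) adds k to both numerator and denominator, which raises any proportion below 1. The literal rate is therefore always the lower once k is at least 1. With N=30, E=4, D=4, k=2 it is 2/26 = 7.7% against 4/28 = 14.3%.

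**The case against.** The strongest reply is that the milder reading is the better one. SAP 10.1 bases percentages on available values, and an adjudicated stroke is an available value. SAP 10.4.1.2 is the more specific text: it counts events over the whole window, in the mITT set. SAP 10.6, the section devoted to missing data, does not mention discontinuers. Table 2 in SAP 10.4.2.2 runs the AE period to the date of early discontinuation, which would serve little purpose if those subjects left the AE percentages. Protocol 4.2.1 uses withdrawn subjects' data, and protocol 9.5 removes subjects from primary safety for non-receipt of the device or lack of post-procedure data, not for later withdrawal.

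Most of this stands as evidence of intent. But SAP 10.1 yields only where something else is specified, and none of these passages is written as an exception for stroke/death. A time window is not a denominator rule: in-stent stenosis has the same cumulative window and was still given its own exclusion sentence.

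It also stands that the consequence is limited. SAP 6 says that the intervals are not for inference. SAP 5.4 requires 12-month follow-up of all enrolled and treated subjects, and protocol 6.3.2 requires a visit after a stroke, so few or no subjects may be affected. The table shells (SAP 11) and the Close Out Plan are separate documents that were not available, and either could settle the point.

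A reader might infer that the rule makes the device look safer, or that one such subject is enough to do so. The documents support neither: the direction depends on whether k exceeds D × E/N, and they give none of these counts.

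**Conclusion.** The point holds as a defect of wording with a possible effect on a primary result. As written, SAP 10.1 can remove an observed, adjudicated non-fatal major stroke from the primary safety percentage, and nothing in the SAP states otherwise. It should be fixed, but no pass/fail decision depends on it.

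The size cannot be derived from the documents and may be nil. On the assumed counts, the literal rate differs from the all-mITT rate by between 2.7 points too high (16.7% against 14.0%) and 5.6 points too low (7.7% against 13.3%).

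Three stronger conclusions are not supported: that strokes will in fact be dropped, since the sponsor probably means to keep them; that deaths are dropped, since SAP 10.2 separates them from discontinuation; and that the bias is downward. Confidence is medium, because the shells and the Close Out Plan were not seen.

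**What to change.** In SAP 10.4.1.2, state that:

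1. Any mITT subject with an adjudicated major ipsilateral stroke or death from the start of the index procedure to completion of the 12-Month Follow-up counts in both numerator and denominator, whether or not the subject later discontinued.
2. Event-free discontinuers are either in or out of the denominator (choose one and say so), and their number is shown beside the rate.

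In SAP 10.1, limit the exclusion of discontinuers to by-visit summaries, and bring 10.6 into line. Apply the same rule to the other cumulative event percentages: AEs, bleeding, recanalization and retreatment.

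This change should not alter the handling of subjects who did not receive the device or who have no post-procedure data. Protocol 9.5 excludes them from the primary safety analysis, whereas the SAP's mITT set is defined by attempted treatment. The two should be reconciled explicitly.

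The cost is a few sentences of SAP text and no new data. The downside is that counting event-free discontinuers in the denominator treats them as event-free to 12 months, so the crude rate can understate the 12-month risk. That is the reason for showing their number.

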10.2 Disposition of Study Subjects

- Disposition

The number and percentage of subjects who are included in and excluded from each analysis set (as defined in Section 7) will be presented, together with a summary of subjects who completed, died or discontinued the study with associated reasons.

10.3 Demographic, Baseline, Aneurysm and Procedure Characteristics

Subject demographics, aneurysms and procedure characteristics will be summarized and listed in mITT analysis set.

10.4 Primary and Secondary Endpoint Analyses

Protocol specified tests of hypotheses of the primary endpoints will not be performed due to the study terminating early for low enrollment. Descriptive analyses of the primary effectiveness and primary safety endpoint will be conducted in the mITT Analysis Set. Categorical data will be summarized with exact binomial confidence intervals for primary effectiveness and safety endpoints. Continuous data will be summarized with averages by visit and as average change from baseline at each visit.

Unless specified otherwise, the classification of adverse events will be based on the data from study case reported forms (CRFs). In the event the data are not captured or are missing, the DSMB and/or CEC adjudication data will be reported.

10.4.1 Primary Endpoints

10.4.1.1 Primary Effectiveness Endpoint

- Rate of RACO at 12 months post-procedure according to the Raymond Scale as assessed by the Independent Core Laboratory.

The number and percentage of subjects with RACO at 12-Month Follow-up will be summarized based on the assessment from the Independent Core Laboratory.

- Subjects who are retreated (retreatment includes staged procedures) prior to 12 months angiographic imaging will be considered as not achieving complete aneurysm occlusion;
- Subjects who have missing values in Raymond Scale at 12-Month Follow-up will be excluded from analysis.

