## 9.5 Handling of Missing Data

Primary effectiveness and primary safety endpoint analyses will be conducted on the modified intent-to-treat (MITT) population, where subjects with missing data at the time of endpoint analysis will be imputed as last observation carried forward (LOCF); see Section 9.8 for analysis set definitions. Note that the immediate post-procedure evaluation will be utilized in this LOCF methodology if this is the last observation on file. MITT subjects who receive the device but in whom there is no post-procedure data will be treated as failures for the purpose of the primary effectiveness endpoint analysis; these subjects will be excluded from all other endpoint analyses. Subjects who do not receive the device because of treatment failure due to reasons associated with the device will also be treated as failures for the primary effectiveness endpoint analysis; these subjects will be excluded from all other endpoint analyses. MITT subjects who do not receive the device because of an intra-operative surgeon decision based on patient anatomy (e.g. vessel tortuosity) will be treated as missing (and not as failures) in all endpoint analyses, including the primary effectiveness and primary safety endpoint analysis.

All subjects who have died prior to an evaluation will have a mRS score of 6 imputed for that time point for analysis purposes.

All other analyses based upon MITT or PP population data will be based upon actual data, with no data imputation.

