5.4 Safety Follow-up after 12 Months Post-Procedure

According to the Close Out Plan, all enrolled and treated subjects will be required to complete follow-up visits through 12 months post-procedure. Hence, only a small number of subjects will have additional safety follow-up data post 12 months. AEs that started after 12-month follow-up will only be listed.

6. Levels of Significance

Protocol specified tests of hypotheses of the primary endpoints at the planned 2.5% significance level will not be conducted due to early termination of the study prior to enrollment of the planned sample size. Two-sided confidence intervals will be computed at a 95% confidence level but are not intended for inference.

7. Analysis Sets

The following analysis sets are defined for the study.

- Modified Intent-to-Treat (mITT) Analysis Set

The mITT Analysis Set consists of all consented (enrolled) subjects who meet all pre-procedure angiographic eligibility criteria, and in whom treatment with the Enterprise device is attempted.

8. Sample Size Justification

This study was originally planned at a total sample size N=320, with an interim analysis for an early stop (either due to futility or tentative success) at N=160 when subjects were enrolled and followed for a minimum of 6-month post-procedure.

However, as the study will be terminated early due to low enrollment, the total sample size for the descriptive analyses in the final CSR will be based on the actual enrollment achieved. .

9. Data and Safety Monitoring Board (DSMB)

An independent DSMB was constituted for monitoring the accumulated interim data as the study progresses to ensure subject safety. All safety review procedures were established and agreed upon in the DSMB Charter prior to enrollment of the first subject.

10. Analyses to be Conducted

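### SAP 10.4.1.1 omits the protocol 9.5 rule that non-implantation for device-related reasons is a primary effectiveness failure, so a failed delivery can drop out of the reported mITT rate

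*SAP*

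**What the plan says.** Protocol 9.5 sets out how incomplete treatment or data enter the primary effectiveness analysis. On failed delivery it says: "Subjects who do not receive the device because of treatment failure due to reasons associated with the device will also be treated as failures". The Overview (Sample Size Determination) and section 3.1 repeat this. Anatomy-based non-implantation is handled differently: a subject not implanted because of "an intra-operative surgeon decision based on patient anatomy (e.g. vessel tortuosity) will be treated as missing". A third rule concerns implanted subjects: "MITT subjects who receive the device but in whom there is no post-procedure data will be treated as failures". It sits beside the carry-forward (LOCF) scheme, for which the protocol adds: "Note that the immediate post-procedure evaluation will be utilized in this LOCF methodology if this is the last observation on file".

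The SAP's mITT set (section 7) takes angiographically eligible subjects "in whom treatment with the Enterprise device is attempted", so implantation is not required. For the primary effectiveness rate, SAP 10.4.1.1 gives two rules: "Subjects who are retreated (retreatment includes staged procedures) prior to 12 months angiographic imaging will be considered as not achieving complete aneurysm occlusion", and "Subjects who have missing values in Raymond Scale at 12-Month Follow-up will be excluded from analysis". SAP 10.1 adds: "Unless specified otherwise, percentages are based on non-missing values, excluding missing data and subjects who early discontinued". SAP 10.6 rules out imputation unless stated otherwise, and 10.7 plans no sensitivity analysis. SAP 5.1.1 defines success as a Raymond score of 1 without a further procedure on the aneurysm. It does not require that the study stent was implanted. The protocol's rule on device-related non-implantation appears nowhere in the SAP.

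**The concern.** Treating failed delivery as a failure is what makes an attempted-treatment population meaningful: if the device cannot be placed, that should count against it. Without the rule, the rate keeps the mITT label, but some of the least favourable cases may be missing from it.

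The SAP explains the absence of tests and of an interim analysis by early termination for low enrolment. It gives no such reason for dropping this rule, which needs no minimum sample size. Because nothing is tested, the reported rate and its exact interval are the whole primary effectiveness result, so how the denominator is formed deserves care.

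**Working it through.** **1. What happens to an mITT subject not implanted for device-related reasons**

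The protocol keeps entered subjects on the 12-month angiogram schedule whatever treatment follows (4.0, 6.3.6), so a score may exist. SAP 5.4 reports the Close Out Plan as covering enrolled and treated subjects. It does not say whether a non-implanted subject is treated, so a score is not assured.

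| Situation at 12 months | Protocol 9.5 | SAP 10.4.1.1 |
|---|---|---|
| Score 2 or 3, no retreatment | failure | failure |
| Treated in a later session | failure | failure by the retreatment rule, if that rule takes precedence |
| No score, no retreatment | failure | removed from the denominator |
| Score 1, no retreatment | failure | success |

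Row 2: Appendix 1 of the protocol defines the index procedure as the session in which stenting is attempted, and SAP 5.2.1 counts any later treatment of the target aneurysm as retreatment. Protocol 4.0 says that retreated aneurysms are not assessed for effectiveness afterwards, so a missing score is likely. The SAP does not say whether the retreatment rule overrides the missing-score exclusion or the exclusion of early discontinuations in 10.1.

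Row 4: this needs treatment in the same session without the study stent. Protocol 6.2.2 and 6.2.3 require coils to be placed after stent deployment, so it would be a departure from protocol and should be rare.

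**2. Direction**

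Let N be the number analysed when affected subjects count as failures, and x the number of successes. Of the affected subjects, a are removed and b score 1. The protocol rule gives x/N. The SAP gives (x + b)/(N - a), which is never below x/N and equals it when a = b = 0. This holds with all other subjects handled the same way under both rules.

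**3. How many subjects might be affected**

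Neither the final N nor the number of failed deliveries is in the documents. The earlier studies in protocol 1.3 are a rough guide to non-implantation for any reason:

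- Europe: 0 of 31.
- United States: 0 of 28 (two others were disqualified angiographically).
- Argentina: 0 of 10.
- Sunrise registry: 1 of 109 untreated, reason not stated.

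Pooled: 31 + 28 + 10 + 109 = 178, so at most 1/178 = 0.56%, with an exact (Clopper-Pearson) 95% upper limit of 3.09%.

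**4. Size**

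If a share f is removed, a rate p under the protocol rule becomes p/(1 - f). Take p = 44%, a design value from the protocol's power table:

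- f = 1/178: 0.44/(1 - 1/178) = 44.2%
- f = 3%: 0.44/0.97 = 45.4%
- f = 7%: 0.44/0.93 = 47.3%. This is a planning ceiling only, because the 7% in protocol 3.1 covers all exclusions, including anatomy-based ones.

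One affected subject, with assumed N (exact 95% intervals in brackets):

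| N | Counted as failure | Removed | Counted as success |
|---|---|---|---|
| 100 | 44/100 = 44.0% (34.08 to 54.28) | 44/99 = 44.4% (34.45 to 54.78) | 45/100 = 45.0% (35.03 to 55.27) |
| 50 | 22/50 = 44.0% (29.99 to 58.75) | 22/49 = 44.9% (30.67 to 59.77) | 23/50 = 46.0% (31.81 to 60.68) |

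One subject thus moves the rate by 0.4 to 1.0 points at N = 100 and 0.9 to 2.0 points at N = 50. The intervals are about 20 and 29 points wide.

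**5. The separate LOCF change**

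The SAP also abandons LOCF for other missing scores. Assume 8% missing and 44% occluded among those scored. Carrying forward at the registry's acute rate of 20.2% gives 0.92 x 0.44 + 0.08 x 0.202 = 42.1%. At its 6-month rate of 58.2% it gives 0.92 x 0.44 + 0.08 x 0.582 = 45.1%. That change can go either way and is not part of this point.

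**The case against.** The strongest reply is that little is left once the SAP's other rules have acted. A later-session treatment is already a failure, a score of 2 or 3 is a failure, and a score of 1 without the study stent requires a protocol departure. That is right, and it is why the effect is small. Removal of an unscored, unretreated failed delivery remains, and no other SAP clause prevents it.

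Second, failed deliveries are not hidden. SAP 10.2 reports discontinuations with reasons, 10.3 summarises procedure characteristics (which protocol 9.10.3 takes to include attempted and successful procedures), and 10.4.2.1 reports acute procedure success. The table shells and the Close Out Plan are not available and may contain more. This lessens the harm but does not change the primary rate.

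Third, separating device-related from anatomical reasons takes judgement in an unblinded study, whereas excluding missing scores is mechanical. This stands as a cost. Protocol 9.5 gives tortuosity as an anatomical reason, while Appendix 1 gives failure to reach the target site as a device-related complication.

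A reader might also infer that the rule for implanted subjects without post-procedure data must come back. The documents do not support that. It is the leftover case of the LOCF scheme, for subjects with nothing to carry forward. Restored alone, it would fail a subject with no angiogram while excluding one with only an acute angiogram. The group should also be nearly empty, because the post-treatment angiogram is taken before the procedure ends (Table 1, note 10).

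**Conclusion.** The point holds for device-related non-implantation. SAP 10.4.1.1 drops a protocol failure rule without saying so. With other subjects handled alike, the reported mITT rate is then equal to or higher than under the protocol rule. From an assumed 44%, the shift is about 0.4 to 2 points per affected subject at an assumed N of 50 to 100, and zero if there is no such subject or if all of them score 2 or 3 or are counted as retreated. The earlier studies suggest few such subjects, but the one untreated registry subject has no stated reason and may not have been a failed delivery.

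Two stronger readings are tempting and are not supported. One is that the SAP as a whole inflates the rate relative to the protocol: dropping LOCF can move it in either direction and by more. The other is that a success conclusion is at risk: the SAP runs no tests and says that its intervals are not for inference. What is affected is a descriptive rate and how it is read.

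**What to change.** In SAP 10.4.1.1, state an order of rules that overrides 10.1 and 10.6:

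1. Subjects retreated before the 12-month imaging are not occluded, whether or not a score exists.
2. mITT subjects not implanted for device-related reasons, as recorded on the eCRF, are not occluded, whether or not a score exists.
3. Only the remaining missing scores are excluded, with counts by reason. Anatomy-based non-implantation is one of those reasons, as in protocol 9.5.

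Before any subject is classified, the sponsor should reconcile protocol 9.5 with Appendix 1 on failed access in a tortuous vessel and write the rule down. For implanted subjects with no post-procedure data, it is enough to state the departure from protocol 9.5 and report how many there are.

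The cost is a few lines of SAP text, a count by reason, and a small classification step. The source exists, since Appendix 1 has device-related technical complications recorded on the eCRF. The reported rate may be slightly less favourable. If no subject was left unimplanted for device-related reasons, one sentence saying so closes the matter.
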